Appendix 2 Bristol Stool Scale

Appendix 3 Brief Pain Inventory-Short Form – English version (24 h)

Appendix 4 Patient Global Impression questionnaires

Patient Global Impression of Severity of neuropathic Pain (PGIS-P)

The following question refers to the neuropathic pain you may experience due to your Fabry disease.

Please choose the response that best describes the overall severity of the neuropathic pain you may have experienced due to your Fabry disease over the past 7 days (week):

- 1=None
- 2=Mild
- 3=Moderate
- 4=Severe

Patient Global Impression of Change in neuropathic Pain Severity (PGIC-PS)

The following question refers to the neuropathic pain you may experience due to your Fabry disease.

Please choose the response that best describes the change in the overall severity of the neuropathic pain you may have experienced due to your Fabry disease since you started study treatment:

- 1 = Very Much Improved
- 2 = Much Improved
- 3 = Minimally Improved
- 4 = No change
- 5 = Minimally worse
- 6 = Much Worse
- 7 = Very Much Worse

Patient Global Impression of Severity of Disease (PGIS-D)

The following question refers to symptoms (e.g., neuropathic pain, abdominal pain, diarrhea, constipation) you may experience due to your Fabry disease.

Please choose the response that best describes the overall severity of the symptoms you may have experienced due to your Fabry disease over the past 7 days (week):

-
- 1=None
 - 2=Mild
 - 3=Moderate
 - 4=Severe

Patient Global Impression of Change in Disease Severity (PGIC-DS)

The following question refers to symptoms (e.g., neuropathic pain, abdominal pain, diarrhea, constipation) you may experience due to your Fabry disease.

Please choose the response that best describes the change in overall severity of the symptoms you may have experienced due to your Fabry disease since you started study treatment:

- 1 = Very Much Improved
- 2 = Much Improved
- 3 = Minimally Improved
- 4 = No change
- 5 = Minimally worse
- 6 = Much Worse
- 7 = Very Much Worse

Appendix 5 Center for Epidemiologic Studies Depression Scale Revised

Center for Epidemiologic Studies Depression Scale – Revised (CESD-R)

Below is a list of the ways you might have felt or behaved. Please check the boxes to tell me how often you have felt this way in the past week or so.	Last Week				Nearly every day for 2 weeks
	Not at all or Less than 1 day	1 - 2 days	3 - 4 days	5 - 7 days	
My appetite was poor.	0	1	2	3	4
I could not shake off the blues.	0	1	2	3	4
I had trouble keeping my mind on what I was doing.	0	1	2	3	4
I felt depressed.	0	1	2	3	4
My sleep was restless.	0	1	2	3	4
I felt sad.	0	1	2	3	4
I could not get going.	0	1	2	3	4
Nothing made me happy.	0	1	2	3	4
I felt like a bad person.	0	1	2	3	4
I lost interest in my usual activities.	0	1	2	3	4
I slept much more than usual.	0	1	2	3	4
I felt like I was moving too slowly.	0	1	2	3	4
I felt fidgety.	0	1	2	3	4
I wished I were dead.	0	1	2	3	4
I wanted to hurt myself.	0	1	2	3	4
I was tired all the time.	0	1	2	3	4
I did not like myself.	0	1	2	3	4
I lost a lot of weight without trying to.	0	1	2	3	4
I had a lot of trouble getting to sleep.	0	1	2	3	4
I could not focus on the important things.	0	1	2	3	4

REFERENCE: Eaton, W. W., Smith, C., Ybarra, M., Muntaner, C., Tien, A. (2004). Center for Epidemiologic Studies Depression Scale: review and revision (CESD and CESD-R). In ME Maruish (Ed.). *The Use of Psychological Testing for Treatment Planning and Outcomes Assessment* (3rd Ed.), Volume 3: Instruments for Adults, pp. 363-377. Mahwah, NJ: Lawrence Erlbaum.

Appendix 6 36-Item Short Form Health Survey Version 2

## LIST OF ABBREVIATIONS AND ACRONYMS

$\alpha$ -GalA	$\alpha$ -galactosidase A
AE	Adverse event
ANCOVA	Analysis of covariance
ARRT	Annualized rate of days with significant rescue therapy
AUC <math>\tau</math>	Area under the plasma concentration-time curve during one dosing interval
BLQ	Below the limit of quantification
BPI-SF	Brief Pain Inventory-Short Form
BPI-SF3	Brief Pain Inventory-Short Form item 3
bpm	Beats per minute
BSA	Body surface area
BSS	Bristol Stool Scale
CDISC	Clinical Data Interchange Standards Consortium
CESD-R-20	Center for Epidemiologic Studies Depression revised scale
CI	Confidence interval
CKD-EPI	Chronic Kidney Disease Epidemiology Collaboration
C max	Maximum plasma concentration
CMH	Cochran-Mantel-Haenszel
COVID-19	Coronavirus disease 2019
CR	Copy Reference
CV	Coefficient of variation
DBP	Diastolic blood pressure
DSM	Diagnostic and Statistical Manual of Mental Disorders
eCDF	Empirical cumulative distribution function
ECG	Electrocardiogram
eCRF	Electronic case report form
eDiary	Electronic diary
eGFR	Estimated glomerular filtration rate
EOS	End-of-Study
EOT	End-of-Treatment
ePDF	Empirical probability density function

---

ERT	Enzyme replacement therapy
FAS	Full analysis set
FD	Fabry disease (Anderson-Fabry disease)
FDA	US Food and Drug Administration
FU	Follow-up
Gb3	Globotriaosylceramide
GI	Gastrointestinal
GlcCer	Glucosylceramide (Gb1)
HR	Heart rate
ICE	Intercurrent event
IRT	Interactive Response Technology
J2R	Jump to Reference
$\lambda_z$	First order rate constant associated with the terminal log-linear portion of the plasma concentration-time curve
LacCer	Lactosylceramide (Gb2)
LVMl	Mass-l left ventricle
lysoGb3	Globotriaosylsphingosine
MAP	Mean arterial pressure
MAR	Missing at random
MedDRA	Medical Dictionary for Regulatory Activities
mFAS	Modified full analysis set
mFAS-GIS	Modified full analysis set-gastrointestinal symptoms
MI	Multiple imputation
MMRM	Mixed model for repeated measures
MNAR	Missing not at random
NRS-11	11-point numerical rating scale
OLE	Open-label extension
OR	Odds ratio
ORc	Common odds ratio
PGIC	Patient Global Impression of Change
PGIC-DS	Patient Global Impression of Change in Disease Severity
PGIC-PS	Patient Global Impression of Change in neuropathic Pain Severity

PGIS	Patient Global Impression of Severity
PGIS-D	Patient Global Impression of Severity of Disease
PGIS-P	Patient Global Impression of Severity of neuropathic Pain
PK	Pharmacokinetic(s)
PPS	Per-protocol analysis set
PTOP	Post-treatment observation period
QTc	Corrected QT interval
QTcB	QT corrected according to Bazett's formula
QTcF	QT corrected according to Fridericia's formula
ROC	Receiver operating characteristic
SAE	Serious adverse event
SAF	Safety set
SAP	Statistical analysis plan
SBP	Systolic blood pressure
SCR	Screened analysis set
SD	Standard deviation
SE	Standard error
SI	Standard international
SNRI	Serotonin-norepinephrine re-uptake inhibitor
SOC	System organ class
SOP	Standard Operating Procedures
SSRI	Selective serotonin re-uptake inhibitor
$t_{1/2}$	Apparent terminal elimination half-life
TCA	Tricyclic antidepressant
TEAE	Treatment-emergent adverse event
$t_{max}$	Time to reach maximum plasma concentration
UACR	Urine albumin-to-creatinine ratio
US	United States

## 1 INTRODUCTION

This statistical analysis plan (SAP), based on global protocol version 5 of 24 August 2021 (and local protocol version 5.VHP.B of 25 August 2021), describes in detail the analyses and presentation for the clinical study report for ID-069A301 (MODIFY) of the primary, secondary and exploratory efficacy endpoints as well as all safety endpoints, quality of life endpoints, pharmacokinetic (PK) endpoints, and biomarker endpoints.

This SAP does not cover the analysis of the exit interview sub-study.

Source data for the analyses will be provided as SAS® datasets according to the Clinical Data Interchange Standards Consortium (CDISC) Study Data Tabulation Model. Analysis datasets will be derived as SAS® datasets according to the CDISC Analysis Data Model.

The Clinical Pharmacologist performs the calculation of PK parameters and creates figures of individual and mean concentration-time profiles. PK concentration data will be merged with the actual date/time of sampling by Idorsia Data Management.

## 2 STUDY DESIGN AND FLOW

This is a prospective, multi-center, double-blind, randomized, placebo-controlled, parallel-group, Phase 3 study.

118 adult subjects with Fabry disease (FD) exhibiting Fabry-associated pain of moderate to severe intensity were randomized in a 2:1 ratio to either lucerastat (approximately 79 subjects) or placebo (approximately 39 subjects).

Treatment allocation was stratified by

- sex
- and
- enzyme replacement therapy (ERT) treatment status at screening
    - “pseudo-naïve” / “treatment naïve” (not treated in last 6 months / never treated)
- vs
- “switch” (subjects treated with ERT at screening).

Once randomized, subjects entered a 6-month, double-blind treatment period. Approximately 36 subjects were included worldwide in a PK profile sub-study.

All English-speaking subjects in the US and Canada were asked to participate in an exit interview sub-study; subjects who accepted performed this interview as soon as possible after the Month 6 or End-of-Treatment (EOT) visit, ideally within 2 weeks.

No interim analysis was planned.

## 2.1 Study periods

The study comprises the following consecutive periods as described in section 3.1.1 of the protocol:

**Screening period:** Lasts approximately 6–7 weeks; starts with the signing of the informed consent form (screening visit) and ends with the day before subject randomization. During this period, the subjects will start completing an electronic diary (eDiary) on a daily basis.

**Treatment period (double-blind):** Lasts approximately 6 months, starts on the day of subject randomization (randomization visit) and ends at the EOT visit. It will consist of site visits at Month 1, 3, 5 and 6 and telephone call visits at Month 2 and 4.

The EOT visit will take place at Month 6 (or earlier in the event of premature treatment discontinuation). Whenever possible, the EOT visit should take place 1 day after the last dose of study treatment but no later than 7 days after the last dose of study treatment.

**Post-treatment observation period (PTOP):** Subjects who discontinue study treatment prematurely will enter the PTOp which starts on the day after the last dose of study treatment and ends at the latest at the Month 6 PTOp visit. During this period, all assessments except PK will be performed. They will be performed at the time of the originally scheduled visits.

**Post-treatment safety follow-up (FU) period:** The FU period is applicable to all subjects except those who enter the open-label extension (OLE) study. It starts on the day after the last dose of study treatment:

- For female and non-fertile male subjects: it includes 1 safety FU telephone call (FU1) taking place approximately 1 month after the last dose of study treatment.
- For fertile male subjects: it includes 2 safety FU telephone calls taking place approximately 1 month (FU1) and 3 months (FU2) after the last dose of study treatment.

Subjects who complete the 6-month, double-blind treatment period will be offered enrollment into an OLE study conducted under a separate protocol (provided the OLE study protocol has been approved in the country/site by regulatory authorities and Ethics Committees / Institutional Review Boards).

Subjects who discontinue study treatment prematurely for any reason should be subsequently treated according to local standard-of-care at the investigator's discretion and will be followed in the PTOp until the originally scheduled Month 6 visit.

[figure not shown]
For an individual subject, the End-of-Study (EOS) is defined as follows:

- For subjects who enter the OLE study, the EOS corresponds to the EOT visit.
- For all other subjects, the EOS corresponds to the FU1 visit, the FU2 visit or to the last visit of the PTOp, whichever is last.

The visit schedule and protocol-mandated procedures will be performed according to table 4 and table 5 of the protocol and are described in protocol section 7.1.

The overall study design is depicted in Figure 1.

**Figure 1 Study design**

\* All subjects not entering the OLE study

\*\* Only fertile male subjects not entering the OLE study

\*\*\* Exit interview conducted as soon as possible after the end of study treatment phase (or EOT visit), ideally within 2 weeks

D = day; eDiary = electronic diary; EOT = End-of-Treatment; EOS = End-of-Study; FU = follow-up (telephone); M = month; OLE = open-label extension; PK = pharmacokinetic(s); PTOp = post-treatment observation period; V = visit.

## 2.2 Study duration and global end of study

The study starts with the first subject, first visit and ends with the last subject, last visit. The study is expected to last approximately 3.5 years.

The duration of participation in the study of a subject is expected to be about 9 months for a female subject and about either 9 or 11 months for a male subject.

The global end of the study corresponds to the last visit of the last subject:

- If the last subject enters the OLE study, the global end of the study corresponds to the last subject's EOT visit.
- If the last subject does not enter the OLE study, the global end of the study corresponds to the last subject's FU1 visit, FU2 visit, or to the last visit of the PTOP, whichever is last.

## 3 OBJECTIVES

### 3.1 Primary objective

The primary objective of the study is to determine the effect of lucerastat on neuropathic pain in subjects with FD.

### 3.2 Secondary objectives

- To determine the effects of lucerastat on gastrointestinal (GI) symptoms (abdominal pain and diarrhea) in subjects with FD and GI symptom(s) at baseline.
- To confirm the effect of lucerastat on biomarkers of FD.
- To determine the safety and tolerability of lucerastat in subjects with FD.

### 3.3 Other objectives

- To evaluate the effect of lucerastat on renal function and cardiac parameters in subjects with FD.
- To evaluate the effect of lucerastat on depression in subjects with FD.
- To evaluate the effect of lucerastat on quality of life in subjects with FD.
- To document the PK of lucerastat in subjects with FD.

### 3.4 Efficacy estimands

The estimands targeted by the primary and secondary efficacy objectives and analyses are defined in [Table 1](#).

A treatment policy strategy will be applied for all estimands defined in [Table 1](#), i.e., all collected endpoint data are used in the analyses regardless of occurrence of any intercurrent events (ICEs). Expected ICEs are premature treatment discontinuation as well as use of other medications.

Fabry disease medications (e.g., ERT) are forbidden by the protocol as they are not part of the treatment condition of interest [see definition in [Table 1](#)]. However, considering that forbidden medications could be taken in clinical practice, data collected during use of forbidden medications will be included in the analyses.

**Table 1**      **Estimands for the primary and secondary efficacy objectives and analyses**

Estimand	Target population	Treatment condition of interest	Endpoint	Strategy for addressing intercurrent events	Population-level summary
Primary Estimand	Adult subjects with FD as defined by the inclusion and exclusion criteria in the study protocol.	Lucerastat (dose ranging from 250 mg to 1000 mg b.i.d. based on subject's eGFR value) as monotherapy which will be compared to placebo.	Change from baseline to Month 6 in the modified BPI-SF3 score of "neuropathic pain at its worst in the last 24 hours".	Treatment policy, i.e., all collected endpoint data are used regardless of premature treatment discontinuation or use of other medication (e.g., pain medication, ERT).	Mean change from baseline to Month 6, summarized as the difference between lucerastat and placebo.
Secondary Estimand #1	Adult subjects with FD as defined by the inclusion and exclusion criteria in the study protocol.	Lucerastat (dose ranging from 250 mg to 1000 mg b.i.d. based on subject's eGFR value) as monotherapy which will be compared to placebo.	Change from baseline to Month 6 in plasma Gb3.	Treatment policy, i.e., all collected endpoint data are used regardless of premature treatment discontinuation or use of other medication (e.g., pain medication, ERT).	Mean change from baseline to Month 6, summarized as the difference between lucerastat and placebo.
Secondary Estimand #2	Adult subjects with FD as defined by the inclusion and exclusion criteria in the study protocol with GI symptoms at baseline.	Lucerastat (dose ranging from 250 mg to 1000 mg b.i.d. based on subject's eGFR value) as monotherapy which will be compared to placebo.	Change from baseline to Month 6 in the NRS-11 score of "abdominal pain at its worst in the last 24 hours".	Treatment policy, i.e., all collected endpoint data are used regardless of premature treatment discontinuation or use of other medication (e.g., pain medication, ERT, GI symptomatic treatments).	Mean change from baseline to Month 6, summarized as the difference between lucerastat and placebo.
Secondary Estimand #3	Adult subjects with FD as defined by the inclusion and exclusion criteria in the study protocol with GI symptoms at baseline.	Lucerastat (dose ranging from 250 mg to 1000 mg b.i.d. based on subject's eGFR value) as monotherapy which will be compared to placebo.	Change from baseline to Month 6 in the number of days with at least 1 stool of a Bristol Stool Scale consistency Type 6 or 7.	Treatment policy, i.e., all collected endpoint data are used regardless of premature treatment discontinuation or use of other medication (e.g., medication used to treat/prevent diarrhea).	Win ratio of change from baseline to Month 6 between lucerastat and placebo.

b.i.d. = twice daily; BPI-SF3 = Brief Pain Inventory – Short Form item 3; eGFR = estimated glomerular filtration rate; ERT = enzyme replacement therapy; FD = Fabry disease; Gb3 = globotriaosylceramide; GI = gastrointestinal; NRS-11 = 11-point numerical rating scale.

## 4 ANALYSIS SETS

### 4.1 Definitions of analysis sets

#### 4.1.1 Screened analysis set

The Screened analysis set (SCR) includes all subjects who are screened and have a subject identification number.

#### 4.1.2 Full analysis set

The Full analysis set (FAS) includes all subjects randomized to either lucerastat or placebo.

In order to adhere to the intent-to-treat principle:

- Subjects will be evaluated according to their assigned study treatment (not actual treatment received) and stratum information as recorded in the Interactive Response Technology (IRT) system.
- Unless otherwise stated, all available efficacy data for the primary and secondary endpoints will be included in the analyses up to the planned analysis time point, regardless of study treatment discontinuation and/or switches to alternative FD treatments.

#### 4.1.3 Modified full analysis set

A modified FAS (mFAS) will be defined by including subjects from the FAS who took at least one dose of study treatment. As in the FAS, subjects will be analyzed based on the assigned study treatment.

#### 4.1.4 Modified full analysis set – gastrointestinal symptoms

The mFAS-GI symptoms (mFAS-GIS) comprises all subjects from the mFAS who, during the 4 weeks prior to randomization, have experienced:

- abdominal pain of moderate to severe intensity at baseline defined as an average abdominal pain intensity score  $\geq 3$  on a 11-point numerical rating scale (NRS-11) scale; and/or
- diarrhea at baseline defined as having at least 1 stool of Bristol Stool Scale (BSS) consistency Type 6 or 7 on at least 8 days.

#### 4.1.5 Per-protocol analysis set

The Per-protocol analysis set (PPS) comprises all subjects from the mFAS without protocol deviations occurring prior to Month 6, which could affect the analysis of the primary endpoint variable.

The precise reasons for excluding subjects from the PPS will be fully defined and documented in a separate document that will be finalized and stored in the eTMF before breaking the randomization blind.

#### **4.1.6 Safety set**

The Safety set (SAF) includes all subjects who received at least one dose of study treatment (as recorded in the eCRF). Subjects will be analyzed based on the treatment received. In the situation of accidental dispensation of both treatments to the same patient, the patient will be counted as on lucerastat for the whole study.

#### **4.1.7 PK trough set**

The PK trough set is the subset of the SAF including all subjects who have at least one PK trough sample collected after initiation of lucerastat treatment, had evaluable plasma concentrations, and did not deviate from the protocol in a way that might affect the evaluation of the PK endpoint.

The reason for excluding a subject or a PK trough sample from analysis will be documented by the Idorsia Clinical Pharmacologist before breaking the randomization blind.

#### **4.1.8 PK sub-study set**

The PK sub-study set is the subset of the SAF including all subjects who received the morning dose of lucerastat at the Month 1 visit, have the pre-dose PK sample and pivotal post-dose PK samples collected for the 12 h PK profile, had evaluable plasma concentrations, and did not deviate from the protocol in a way that might affect the evaluation of the PK endpoints.

The reason for excluding a subject from analysis will be documented by the Idorsia Clinical Pharmacologist before breaking the randomization blind.

### **4.2 Usage of the analysis sets**

The mFAS and the PPS will be used for the analysis of the primary endpoint.

Results based on the PPS will supplement those based on the mFAS to assess the robustness of the treatment effect. These analyses will also be produced on the FAS as a sensitivity analysis if FAS and mFAS differ by at least 5 subjects (approximately 5% of the total sample size).

The secondary endpoints related to abdominal pain and diarrhea will be assessed on the mFAS-GIS.

All safety data will be analyzed using the SAF.

The following table provides an overview of the usage of the different analysis sets.

**Table 2 Overview of the different analysis sets and their usage**

	FAS	mFAS	mFAS-GIS	PPS	SAF	PK trough set	PK sub-study set
Demographics, baseline and disease characteristics	✓	✓ a	✓	✓			
Fabry disease history	✓	✓ a					
Other medical history	✓	✓ a					
Previous and concomitant therapies					✓		
Treatment exposure					✓		
Efficacy observation period		✓					
Primary efficacy endpoint	✓ a	✓		✓			
Secondary efficacy endpoints related to abdominal pain and diarrhea		✓	✓				
Other secondary efficacy endpoint (Gb3)		✓					
Exploratory efficacy endpoints		✓					
Safety endpoints					✓		
Quality of life endpoints		✓					
PK trough analysis						✓	
PK profile sub-study							✓
Biomarker endpoints		✓					

a if FAS and mFAS differ by at least 5 subjects

FAS = Full analysis set; Gb3 = globotriaosylceramide; mFAS = Modified full analysis set; mFAS-GIS = Modified full analysis set – gastrointestinal symptoms; PK = pharmacokinetic(s); PPS = Per-protocol analysis set; SAF = Safety set.

## 5 GENERAL DEFINITIONS AND DERIVATIONS

### 5.1 Dates

‘**Randomization date**’ is taken from the date of the randomization visit (V2) recorded in the eCRF. Subjects for whom the date of the randomization visit does not match the date recorded in the IRT system will be listed.

The ‘**Start of treatment date / First study treatment intake date**’ is defined as the date the first dose of study treatment was received (lucerastat or placebo) as documented in the eCRF study treatment log.

The ‘**EOT date**’ is defined as the date of the last dose of study treatment intake as documented in the eCRF study treatment log. In case of incomplete date of the last dose of study treatment intake in the study treatment log of a subject having reached EOS, the EOT

date will be imputed with the latest possible date compatible with the incomplete date, while not being later than EOS.

The ‘EOS date’ will be taken from the eCRF end of study status form. If this date is missing, the last recorded visit or telephone call on the eCRF is considered as the EOS date.

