5.1.7.2 Study treatment compliance

Treatment compliance will be assessed based on eDiary data.

The study treatment compliance with the prescribed study treatment dose regimen will be assessed by the sponsor based on eDiary data. On each day, subjects will be asked to enter in the eDiary the number of capsules taken in the morning and evening. The subjects will receive a reminder alarm (through the device) to take their morning and evening doses of study medication.

For each time interval between two visits (i.e., “period”), the eDiary based study treatment compliance will be calculated by the sponsor using the following formula:

eDiary based study treatment compliance = Total number of times the subject took study treatment at the prescribed dose regimen during the period / Total number of times the study treatment should have been taken at the prescribed dose regimen during the period × 100

The prescribed starting dose corresponds to the dose assigned to the subject by the IRT system at randomization visit. In the event of study treatment adjustment [see Section 5.1.2], the prescribed dose corresponds to the new study treatment dose. The starting date of the new study treatment dose will be the date when the investigator/delegate contacts the subject to provide him/her instructions for study treatment adjustment.

The period is defined as the number of days between visit n (or date of first study treatment intake if randomization visit) and visit n+1 (or date of last study treatment intake if EOT visit).

The number of times the study treatment should have been taken at the prescribed dose regimen in a given period is calculated as follows:

- Number of days in the period × 2

Study treatment interruption(s) will be ignored when calculating the study treatment compliance based on the eDiary.

Between visits, study treatment compliance based on the eDiary is expected to be at least 80%. The sponsor will inform the site staff and CRA about any compliance values below 80%. Compliance values below 80% without a medical justification (e.g., AE) and not related to an eDiary completion issue will be considered as a protocol deviation, which will be reported as such to the sponsor by the CRA. In such cases, the investigator must discuss and clarify the reasons for non-compliance with the subject and take appropriate actions to avoid re-occurrence.

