## 8 TREATMENT EXPOSURE / DURATION OF EFFICACY OBSERVATION PERIOD

### 8.1 Duration of exposure and mean daily dose

**Duration of exposure to study treatment (months)** is defined as (Date of last study treatment intake – Date of first study treatment intake + 1 [in days]) / (365.25/12), regardless of any treatment interruptions. If the first study treatment intake is on the same day as the randomization date, the duration of exposure is reduced by 0.5 day. If the last study treatment intake is on the same day as the Month 6 visit, the duration of exposure is reduced by 0.5 day.

Treatment dates will be taken from the eCRF study treatment log.

The study treatment is administered b.i.d., i.e., the daily dose of a given day is twice the dose (mg) recorded in EX.EXDOSE if this is a day without dose change. A day with dose change is identified when being simultaneously the last day of a constant-dosing interval of EX and the first day of the next constant-dosing interval; in that situation, the daily dose is the sum of the two distinct doses. On days without dose change, if the dose frequency is reported as QD or ONCE, only one dose is counted on the respective day.

Only one dose (the evening dose) is counted on Treatment Day 1 (unless the first study treatment intake is not on the same day as the randomization date; in this situation two doses are counted on Treatment Day 1). Only one dose is counted on the EOT date (unless the last study treatment intake is not on the same day as the Month 6 visit; in this situation two doses are counted on the EOT date).

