#### **8.4 Duration of efficacy observation period**

**Duration of efficacy observation period (months)** is defined as (date of last visit performed up to Month 6 [including unscheduled visits and EOT visit if applicable; if no such visit is available, the EOT date will be used] – Randomization date + 1 [in days]) / (365.25/12).

**Duration of PTOP (months)** is defined as (last PTOP visit date – [EOT date + 1 day] + 1 [in days]) / (365.25/12).

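### SAP 5.1 caps an incomplete last-dose date at End-of-Study rather than at the EOT visit, so for subjects outside the extension the imputed last dose can fall in off-drug follow-up

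*SAP*

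**What the plan says.** SAP 5.1 (Dates) says that the EOT date "is defined as the date of the last dose of study treatment intake as documented in the eCRF study treatment log". Where that date is incomplete for a subject who has reached EOS, the EOT "date will be imputed with the latest possible date compatible with the incomplete date, while not being later than EOS". EOS is the only upper limit given.

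SAP 2.1 (Study periods) sets EOS equal to the EOT visit for subjects who enter the open-label extension. For everyone else "the EOS corresponds to the FU1 visit, the FU2 visit or to the last visit of the PTOp, whichever is last". The same section asks for the EOT visit, whenever possible, "1 day after the last dose of study treatment but no later than 7 days after the last dose of study treatment". Subjects who stop early are followed in the PTOP to their originally scheduled Month 6. The extension is offered to subjects who complete the 6-month treatment period.

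The last-dose date then feeds:

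- exposure, taken from first to last intake "regardless of any treatment interruptions" (SAP 8.1), and the subject-years built from it (SAP 14.5);
- the number of doses due in the last compliance period (SAP 8.3);
- PTOP duration, which runs from the day after the EOT date to the "last PTOP visit date" (SAP 8.4);
- the treatment-emergent window, which closes at EOT + 30 days (SAP 10, and the Month 6 row of SAP Table 15).

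**The concern.** The cap should stop an imputed last dose from running past the point where the subject is known to be off drug. For extension entrants it does, because EOS and the EOT visit coincide. For all others EOS is a contact that takes place after dosing has ended. The rule can therefore place the last dose later than the visit held to close treatment, and nothing else in either document prevents this.

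Where the rule is triggered, off-drug time is counted as exposure and as subject-years. PTOP time shrinks by the same amount. Days after the EOT visit enter the doses-due count of the last compliance period. Adverse events, laboratory values, vital signs and ECGs collected off drug can be tabulated as treatment-emergent.

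**Working it through.** The documents give no figure for this point, so the check is calendar arithmetic.

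**Inputs**

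- FU1 is 30 to 37 days and FU2 (fertile males) 91 to 105 days after the last dose (Protocol Table 5).
- The Month 6 PTOP visit falls on Day 169 to 197 (Protocol Table 6).
- The EOT visit is at most 7 days after the last dose (SAP 2.1; Protocol 7.1).
- SAP 7.4, for disease-history dates, recognises two kinds of incomplete date: day missing, and day and month missing. SAP 5.1 does not define the term; I assume the same two kinds.

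**Formula.** Imputed EOT date = the earlier of (last date compatible with the partial date) and EOS. Excess = imputed date − true last dose.

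**Only the day missing.** The latest compatible date is the last day of that month, so the excess is at most 31 − 1 = 30 days. An on-schedule FU1 is never earlier than 30 days after the last dose, so the EOS cap never shortens this imputation in a non-extension subject followed per protocol.

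**Day and month missing.** The imputed date is the earlier of 31 December of the recorded year and EOS. The full distance to EOS is reached only if the true last dose and EOS fall in the same calendar year.

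**Averages for early stoppers.** These assume randomization on each day of one calendar year, a true last dose on Study Day 15 to 159, and EOS as the later of Day 183 and the last dose + 37 days (FU1) or + 105 days (FU2).

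| Missing part | Mean excess, SAP rule (days) | Maximum (days) | Mean with cap at an EOT visit 7 days after last dose | Maximum |
|---|---|---|---|---|
| Day | 14.8 | 30 | 6.1 | 7 |
| Day and month | 81.4 (FU1) to 98.8 (FU2) | 168 | 6.9 | 7 |

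The 168 is 183 − 15, so it depends on the assumed range. Completers who do not enter the extension are also exposed: up to 37 days (FU1) or 105 days (FU2) if the month is missing.

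**Worked case.** First dose on Day 1 (evening), true last dose on Day 40, last PTOP visit and EOS on Day 183. One month is 365.25/12 = 30.4375 days.

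- Exposure = (EOT day − 1 + 1 − 0.5)/30.4375
- PTOP = (183 − [EOT day + 1] + 1)/30.4375
- Window end = EOT day + 30

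| Case | EOT date | Exposure (months) | PTOP (months) | Window closes |
|---|---|---|---|---|
| True date | Day 40 | 39.5/30.4375 = 1.30 | 143/30.4375 = 4.70 | Day 70 |
| Capped at EOT visit, 7 days later | Day 47 | 46.5/30.4375 = 1.53 | 136/30.4375 = 4.47 | Day 77 |
| Day missing, 15-day excess | Day 55 | 54.5/30.4375 = 1.79 | 128/30.4375 = 4.21 | Day 85 |
| Day missing, 30-day excess | Day 70 | 69.5/30.4375 = 2.28 | 113/30.4375 = 3.71 | Day 100 |
| Day and month missing, Days 40 and 183 in the same year | Day 183 | 182.5/30.4375 = 6.00 | 0 | Day 213 |

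In the last row, SAP 8.1 might take off a second half day, giving 182/30.4375 = 5.98 months; this changes nothing material.

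**The case against.** The strongest reply is that the bad cases will hardly occur. Every subject who stops should have an EOT visit within 7 days (Protocol 7.1). Returned drug is counted on the visit day (Protocol 5.1.7.1). The dosing times around each PK sample are recorded (Protocol 7.2.6.2), and queries run until database lock (Protocol 11.3). A last dose known only to the year would have to survive all of that. This stands. It limits how often the rule is used, but not what the rule does when it is used.

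A second reply is that late imputation is deliberately inclusive. SAP 10 also counts adverse events with an incomplete onset date as treatment-emergent whenever they could be, and the EOT rule applies to both arms. This stands for event capture. The same date, however, lengthens exposure and shortens the PTOP, where a later date is an error and not caution. A cap at the EOT visit is still a latest-date rule.

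Three stronger readings are tempting and not supported:

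- A reader might infer that early stoppers are routinely credited with months of exposure. A partial date binds: a missing day alone cannot give more than 30 days.
- A reader might infer that early stoppers' last-dose dates are more often incomplete. Neither document says so, and early stoppers have the same EOT visit requirement.
- A reader might infer that the eDiary would normally settle the date, since "subjects will be asked to enter in the eDiary the number of capsules taken in the morning and evening" (Protocol 5.1.7.2). SAP 8.3 instead adds a log-based compliance figure because eDiary completion may be a problem.

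**Conclusion.** The point holds, as a minor one. In non-extension subjects the EOS cap lets an imputed last dose fall after the EOT visit. With only the day missing, the excess is at most 30 days and about 15 on average, given the assumed stop days. An excess of months needs a missing month, and the imputed date cannot pass the end of the recorded year.

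A reader might infer that efficacy results are at risk. They are not: the primary and secondary endpoint analyses use all collected data regardless of treatment discontinuation. Extension entrants are unaffected, and overall compliance (SAP 8.3) runs to the EOT visit, so only the last-period figure is distorted.

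The number of incomplete last-dose dates is not given and may be very small or zero, so no study-level effect on exposure or event counts can be stated. The 7-day bound under the revised cap assumes that the EOT visit is on schedule.

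**What to change.** In SAP 5.1, impute an incomplete last-dose date with the latest date that is compatible with the partial date and not later than the earlier of the EOT visit (Month 6 or premature EOT) and EOS. Use EOS alone only if no EOT visit took place.

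Do not add an eDiary step. Early stoppers are asked to keep completing the eDiary to Month 6 (Protocol 7.2.2.2.4), so if the capsule question stays active, a zero entry could be taken as a dosing day. If entries stop before dosing does, the last dose would be dated too early and real on-treatment events could be lost.

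The cost is one sentence and a small programming change, with no new data. The downside is a slightly less inclusive treatment-emergent window and shorter reported exposure for the few subjects affected.
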